8. TREATMENTS

[figure not shown]
8.1. Treatments Administered

Study drugs will be administered as follows for each cohort in Part 1 of the study:

- Cycle 1 Day -16: single oral dose of G1T38
- Cycle 1 Day -15: no study drug administered
- Cycle 1 Days -14 to -3: oral once-daily doses of osimertinib
- Cycle 1 Day -2: single oral dose of osimertinib and G1T38
- Cycle 1 Day -1: single oral dose of osimertinib

Beginning with Cycle 1 Day 1, oral once-daily doses of G1T38 and osimertinib will commence (Figure 8-1).

Figure 8-1 Study Schema: Part 1

PTV = Post-Treatment visit

There is no Day 0 in the study. A treatment cycle is defined as 28 days.

In Part 2, eligible patients will be randomized (1:1) to receive osimertinib or G1T38 (at the RP2D) + osimertinib. Randomized patients will begin once-daily oral dosing of osimertinib or G1T38 + osimertinib on Cycle 1 Day 1 (Figure 8-2).

Screening Treatment PTV Survival Cycle 1 Day 1 until PD All patients to have All natients to be **Optional Crossover** followed every RECIST 1.1 Osimertinib assessment every Patients begin 8 weeks for PFS and 8 weeks until disease OS until disease post-progression progression G1T38 + osimertinib progression with RECIST assessments every Randomize 8 weeks All patients to have All patients to be RECIST 1.1 followed every G1T38 + 8 weeks for PFS and assessment every Osimertinib 8 weeks until disease OS until disease progression progression

Figure 8-2 Study Schema: Part 2

PTV = Post-Treatment visit

8.1.1. Investigational Medicinal Product (IMP)

G1T38 will be initially supplied initially as oral capsules containing 25 or 100 mg equivalents of G1T38 free base. Excipients used in the formulation include microcrystalline cellulose, hypromellose, mannitol, croscarmellose sodium, and magnesium stearate.

Once available, G1T38 supply will be transitioned to oral tablets containing 50 or 200 mg of G1T38 free base. Excipients used in the tablet formulation include microcrystalline cellulose, hypromellose, croscarmellose sodium, and magnesium stearate. The film coating contains polyethylene glycol: polyvinyl alcohol graft copolymer, talc, titanium dioxide, mono-and di-glycerides, and partially hydrolyzed polyvinyl alcohol.

Alternate strengths may be utilized in the event that they become available.

Packaging and Labeling

G1T38 is packaged in high-density polyethylene (HDPE) bottles and sealed with child-resistant closures. Bottles of G1T38 capsules contain 30 capsules; whereas, bottles of G1T38 tablets contain 35 tablets. Bottles of G1T38 will be labeled and supplied to the investigator or pharmacist/designee who will inventory the contents and document them according to the drug accountability requirements (Section 8.1.4).

Storage

The G1T38 shall be stored at 15°C to 30°C.

Study drugs will be stored in a locked cabinet/secure area under applicable storage conditions at the site and only the pharmacist/designee and designated personnel will have access to the study drugs.

8.1.2. Other Investigational Medicinal Products

8.1.2.1. Osimertinib

A description of the formulation, packaging and labeling for osimertinib can be found in the respective current prescribing information (see Appendix 2).

Store osimertinib bottles at 25°C (77°F). Excursions are permitted to 15°C to 30°C (59°F to 86°F).

8.1.3. Procedure for Dispensing

Dispensing instructions will be provided in the Pharmacy Manual and will be maintained in the pharmacy records.

8.1.4. Investigational Product Accountability

The pharmacist/designee will verify the integrity of the clinical study supplies (storage conditions, correct amount received, condition of shipment, bottle numbers, etc.) according to the investigative site's standard operating procedures (SOPs). Additional requirements may be found in the Pharmacy Manual.

8.2. Method of Assigning Patients to Treatment Groups

A unique patient identification number and allocation to a cohort/treatment group will be assigned by an interactive web-response system (IWRS).

8.3. Dose, Dosing Regimen, and Route

8.3.1. G1T38

The starting dose of G1T38 is 200 mg orally (see Section 4.4.2). Dose escalation/de-escalation is described in Section 6.1.1.1. The maximum G1T38 dose level explored shall not exceed 650 mg per day.

In Part 1, all patients will receive single doses of G1T38 on Cycle 1 Day -16 and Cycle 1 Day -2 and begin continuous G1T38 once-daily dosing on Cycle 1 Day 1 (note: there is no Day 0 in the study). In Part 2, patients randomized to osimertinib with G1T38 will begin G1T38 once-daily continuous oral dosing on Cycle 1 Day 1.

G1T38 should be taken with food. G1T38 should be taken at approximately the same time each day.

8.3.2. Osimertinib

All patients will receive continuous oral osimertinib 80 mg once daily (starting on Cycle 1 Day -14 in Part 1 and on Cycle 1 Day 1 in Part 2).

Osimertinib may be taken with or without food, and should be taken at approximately the same time each day.

Version: 4.0, dated 02 September 2019

8.3.3. Dose Modification

8 3 3 1 G1T38

Dose adjustments of G1T38 for toxicities are to be made according to the organ system showing the greatest degree of drug-related toxicity. Toxicities will be graded using NCI CTCAE, Version 4.03. No more than 2 G1T38 dose level reductions in total are allowed for any patient. Toxicity that requires dose level reduction more than twice will lead to permanent discontinuation of G1T38 dosing for the individual patient.

Since fatigue can be a symptom of cancer progression, dose reduction will only be performed if the fatigue is deemed to be drug related in the opinion of the investigator.

An off-drug period of up to 21 consecutive days is permitted to allow recovery from any toxicity. Off-drug periods of greater than 21 days may be allowed if the investigator believes the potential benefits of continued treatment outweigh the potential risks, but such cases must be discussed with the medical monitor.

Dose Modifications for G1T38-Related Hematologic Toxicity

The G1T38 dose level adjustments in Table 8-1 are based on hematologic adverse reactions, except lymphopenia (unless associated with clinical events, eg, opportunistic infections).

Table 8-1 G1T38 Dose Level Adjustments Based on G1T38-related Hematologic Toxicities

CTCAE Grade of Hematologic Toxicity	G1T38 Dose Adjustment
Grade 3	Continue G1T38 and repeat CBC at next scheduled visit.
≥ Grade 3 neutropenia associated with a documented infection or fever ≥ 38.5°C ≥ Grade 3 thrombocytopenia associated with bleeding	Withhold G1T38 and monitor counts weekly until ANC \geq 1 x 10 ⁹ /L. Resume therapy at the next lower dose. Withhold G1T38 and monitor counts weekly until platelet count \geq 75 x 10 ⁹ /L. Resume therapy at the next lower dose.
Grade 4	Withhold G1T38 and monitor counts weekly until ANC \geq 1 x 10 ⁹ /L and platelet count \geq 75 x 10 ⁹ /L. Resume therapy at the next lower dose.

ANC = absolute neutrophil count; CBC = complete blood count; CTCAE = Common Terminology Criteria for Adverse Events

Granulocyte-colony stimulating factor

The optimal treatment for G1T38-induced neutropenia is to withhold G1T38. Granulocyte-colony stimulating factor (G-CSF) will not work in this setting because G1T38 induces a G1 cell cycle arrest in myeloid precursors that cannot be overcome by G-CSF. Withholding G1T38 treatment will allow neutrophil counts to recover naturally as the study drug concentrations in the body decline and the myeloid precursors are released from G1 arrest and mature to produce neutrophils. If the patient experiences neutropenia lasting

more than 10 days after the cessation of G1T38 and the investigator believes that G-CSF use is clinically indicated, then the investigator must contact the medical monitor to discuss the use of G-CSF.

In the event that the patient experiences a drug-related hematologic toxicity warranting dose reduction, which may be related to G1T38 or osimertinib (ie, the investigator is unable to determine whether the toxicity is related to G1T38 or osimertinib), the investigator shall dose-reduce G1T38 first. If the toxicity does not resolve following the first dose reduction of G1T38, then the investigator shall use clinical judgement to determine if a second G1T38 dose reduction is warranted or if osimertinib dose reduction is warranted. In this situation, discussion with the medical monitor is recommended.

Dose Modifications for G1T38-Related Nonhematologic Toxicity

For any \geq Grade 3 G1T38-related nonhematologic toxicity (excluding alopecia) persisting despite optimal medical treatment, withhold treatment with G1T38 until symptoms resolve to Grade \leq 2 (if not considered a safety risk for the patient). Treatment should be resumed at the next lower dose level of G1T38.

Any patient with liver function test abnormalities meeting Hy's Law criteria (AST or ALT $\geq 3 \times \text{ULN}$ and total bilirubin $\geq 2 \times \text{ULN}$) must have all study drugs permanently discontinued.

Patients with gastrointestinal AEs (eg, nausea, vomiting, diarrhea) may have the total daily dose split, as close to 50:50 as possible, to a morning dose and an evening dose as a means to potentially improved gastrointestinal tolerability. Dose-splitting is not permitted during the DLT evaluation period or the PK evaluation period. In this situation, discussion with the medical monitor is suggested.

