4.2.4. Potential Risks

Based upon nonclinical safety studies at exposures that were at or above the expected exposure in humans, potential adverse effects with G1T38 administration are presented below by body system:

- Blood and lymphatic system disorders: anemia, bone marrow hypocellularity, leukopenia, neutropenia (afebrile or febrile), monocytopenia, lymphopenia, and/or thrombocytopenia
- Infections and infestations: viral and/or bacterial, with the potential to develop sepsis
- Injury and procedural complications: bruising

Palbociclib (IBRANCE®), ribociclib (KISQALI®), and abemaciclib (Verzenio®) are selective CDK4/6 inhibitors for the treatment of hormone receptor (HR)-positive, HER2-negative advanced or metastatic breast cancer in combination with endocrine therapy that have been approved by the United States (US) Food and Drug Administration (FDA). Given the similar mechanism of action to G1T38, the AE profile of G1T38 may be similar to that observed with these 3 compounds. In general, the most common adverse reactions with CDK4/6 inhibitors (incidence ≥ 10%) are neutropenia, infections, leukopenia, fatigue, nausea, stomatitis, anemia, alopecia, diarrhea, thrombocytopenia, rash, vomiting, decreased appetite, asthenia, constipation, headache, back pain, and pyrexia (Palbociclib Prescribing Information 2017; Ribociclib Prescribing Information 2017).

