6.1.1.1. G1T38 Dose Evaluation Criteria

In the first Cohort of 6 patients, a relatively low dose of G1T38 will be administered to allow for a sufficient safety window. This low dose of G1T38 is anticipated to be below the maximum tolerated dose (MTD), even if osimertinib increases the systemic exposure of G1T38 (see Section 4.4.2). However, if ≥ 2 of 6 patients experience a DLT, then the MTD will have been exceeded and a lower G1T38 dose level may be explored. If 1 or fewer patient(s) in the first cohort of 6 experience a DLT, then 3 patients may be enrolled at the next SMC recommended G1T38 dose level.

The G1T38 dose evaluation criteria for Cohorts 2 and beyond are listed below.

- If there is no DLT in a given dose level cohort, then 3 patients may be enrolled at the next SMC recommended G1T38 dose level.
- If there is 1 DLT in a given dose level cohort of 3 patients, an additional 3 patients will be enrolled at this G1T38 dose level. If no additional DLTs are observed (ie, ≤ 1 out of 6 with DLT), escalation may proceed to the next SMC recommended G1T38 dose level.
- If there are \geq 2 DLTs in a given dose level cohort, then the MTD will have been exceeded and a lower G1T38 dose level may be explored as determined by the SMC.

6.1.1.2. Definition of Dose-Limiting Toxicities (Applicable to Cycle 1 Day -16 through Cycle 1 Day 28 in Part 1)

Dose-limiting toxicities are drug-related AEs defined as follows:

- Grade 4 neutropenia
- \geq Grade 3 neutropenic infection/febrile neutropenia
- Grade 4 thrombocytopenia
- ≥ Grade 3 thrombocytopenia with bleeding
- \(\geq \) Grade 3 nonhematologic toxicity (additional criteria for nausea, vomiting, diarrhea, or fatigue: lasting > 5 days with maximal medical management)

• Liver function test abnormalities meeting Hy's Law criteria (aspartate aminotransferase [AST] or alanine aminotransferase [ALT] ≥ 3 × upper limit of normal [ULN] and total bilirubin ≥ 2 × ULN). All study drugs must be permanently discontinued in any patient meeting Hy's Law criteria.

Each patient will be evaluated for toxicity during the Treatment Phase. The toxicity of G1T38 administered with osimertinib will be assessed by the investigators using National Cancer Institute (NCI) CTCAE, Version 4.03.

6.1.2. Part 2

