8.3.3.2. Osimertinib

Dose modifications for osimertinib for adverse reactions are to be made according to Table 8-2.

If a patient experiences a Grade 3 (CTCAE) or higher and/or unacceptable toxicity (any grade), where the investigator considers the AE of concern to be specifically associated with osimertinib (and not attributable to the disease or disease-related processes for which the patient is being treated), dosing will be interrupted and supportive therapy administered as required in accordance with local practice/guidelines.

If a toxicity resolves or reverts to \leq Grade 2 (CTCAE) within 3 weeks of onset, treatment with osimertinib may be restarted at the same dose or a lower dose using the rules below for dose modifications (Table 8-2) and with discussion and agreement with the sponsor's study team physician as needed. There will be no individual modifications to dosing schedule in response to toxicity, only potential dose reduction or dose interruption.

If the toxicity does not resolve to \leq Grade 2 (CTCAE) after 3 weeks, then osimertinib therapy shall be permanently discontinued and the patient shall be observed until resolution or stabilization of the toxicity.

Patients experiencing any of the following AEs will not be permitted to restart osimertinib treatment:

- Corneal ulceration
- Interstitial lung disease (ILD)
- QTc interval prolongation with signs/symptoms of serious arrhythmia
- Symptomatic congestive heart failure or asymptomatic left ventricular dysfunction that persists ≥ 4 weeks
- Liver function test abnormalities meeting Hy's Law criteria (AST or ALT \geq 3 × ULN and total bilirubin \geq 2 × ULN). All study drugs must be permanently discontinued in any patient meeting Hy's Law criteria.

Table 8-2 Recommended Dose Modifications for Osimertinib-Related Adverse Reactions

Target Organ	Adverse Reaction ^a	Dose Modification
Pulmonary	Interstitial lung disease/ pneumonitis	Permanently discontinue osimertinib
Cardiac	QTc interval > 500 msec on at least	Withhold osimertinib until QTc interval is
	2 separate ECGs	< 481 msec or recovery to baseline, then resume
		at 40 mg dose
	QTc interval prolongation with	Permanently discontinue osimertinib
	signs/symptoms of life-threatening	
	arrhythmia	
	Symptomatic congestive heart failure	Permanently discontinue osimertinib
	or asymptomatic left ventricular	
	dysfunction that persists ≥ 4 weeks	
Other	≥ Grade 3 adverse reaction	Withhold osimertinib for up to 3 weeks

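### Table 8-1 covers Grade 4 anemia, but its Grade 4 row lets G1T38 restart on neutrophils and platelets alone, with no hemoglobin or anemia condition

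*Protocol*

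**What the plan says.** Protocol Section 8.3.3.1 introduces Table 8-1 with a scope sentence: "The G1T38 dose level adjustments in Table 8-1 are based on hematologic adverse reactions, except lymphopenia". The one exclusion is itself limited, because lymphopenia with clinical consequences is back in scope.

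The Grade 4 row names no cell line. Its action begins "Withhold G1T38 and monitor counts weekly until ANC" and ends at ANC ≥ 1 × 10⁹/L and platelets ≥ 75 × 10⁹/L, after which G1T38 resumes at the next lower dose.

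The same section adds a general allowance: "An off-drug period of up to 21 consecutive days is permitted to allow recovery from any toxicity". When it is unclear which drug caused a hematologic toxicity, G1T38 is reduced first, and then: "If the toxicity does not resolve following the first dose reduction of G1T38, then the investigator shall use clinical judgement", to choose between a second G1T38 reduction and an osimertinib reduction.

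Anemia is an expected risk. Section 4.2.4 lists the blood disorders as "anemia, bone marrow hypocellularity, leukopenia, neutropenia (afebrile or febrile), monocytopenia, lymphopenia, and/or thrombocytopenia".

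**The concern.** A restart rule should look at the toxicity that caused the hold. For Grade 4 neutropenia or thrombocytopenia this row does so. For Grade 4 anemia it reads two counts that may never have been abnormal. An investigator can follow the table exactly and restart a marrow-suppressive drug with the hemoglobin unchanged. Because no written value says when anemia blocks a restart, two sites could handle the same case differently and both be compliant. What is at stake is patient safety and consistency of conduct, not an estimate or a test.

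**Working it through.** The plan states no figure to reproduce, so the main check sets the rules side by side.

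**1. Is Grade 4 anemia in scope?** Yes. The scope sentence excludes only lymphopenia without clinical consequences. The row above the Grade 4 row names neutropenia and thrombocytopenia, but the Grade 4 row names nothing.

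**2. Does each restart condition measure the cause of the hold?**

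| Reason for hold | Source | Restart condition | Measures the cause? |
|---|---|---|---|
| Grade ≥ 3 neutropenia with infection or fever | Table 8-1 | ANC ≥ 1 × 10⁹/L | Yes |
| Grade ≥ 3 thrombocytopenia with bleeding | Table 8-1 | Platelets ≥ 75 × 10⁹/L | Yes |
| Grade 4 neutropenia or thrombocytopenia | Table 8-1 | Both of the above | Yes |
| Grade 4 anemia | Table 8-1 | Both of the above | **No** |
| Persisting Grade ≥ 3 nonhematologic, G1T38-related | Section 8.3.3.1: "withhold treatment with G1T38 until symptoms resolve to Grade" 2 or lower | Grade ≤ 2 | Yes |
| Grade ≥ 3, attributed to osimertinib | Section 8.3.3.2: "If a toxicity resolves or reverts to" Grade 2 or lower within 3 weeks | Grade ≤ 2, otherwise stop permanently | Yes |

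Attribution therefore matters. Grade 4 anemia blamed on osimertinib must improve to Grade ≤ 2 before osimertinib restarts. The same anemia blamed on G1T38 carries no such condition for G1T38.

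**3. Worked case.** Take a patient whose ANC and platelets stay at the entry limits in Section 7.1.1 (ANC 1.5, platelets 100, both × 10⁹/L) while the anemia reaches Grade 4. Then 1.5 ≥ 1 and 100 ≥ 75, so the restart test is met at the first weekly check. Hemoglobin does not enter it. Neither count bounds hemoglobin, so meeting the test says nothing about the anemia.

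**4. Is the condition elsewhere?** The rest of Section 8.3.3, Section 11.3 and the SAP contain no hemoglobin or anemia condition for restarting G1T38. The only hemoglobin threshold found is the entry criterion of 90 g/L.

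**5. How often could it matter?** Inputs are from Table 4-1 (G1T38-02, G1T38 with fulvestrant, total daily doses 200 to 300 mg, N = 18).
- Related anemia: 6/18 = 33.3% (exact 95% CI 13.3% to 59.0%), all Grade 1-2.
- Related anemia of Grade ≥ 3: 0/18. The exact two-sided 95% upper limit is 1 − 0.025^(1/18) = 18.5%. This limit reflects the small sample and covers Grade 3 as well as Grade 4.
- Related Grade 4 events: 1/18 = 5.6%, a neutropenia, which the row does measure.

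The documents give no Grade 4 anemia rate for G1T38 with osimertinib, or at doses up to the 650 mg ceiling, so I claim no probability.

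**6. Dose at restart.** If the next lower dose follows Table 6-1, the steps are 500/650 = 76.9%, 400/500 = 80.0%, 300/400 = 75.0%, 200/300 = 66.7%, 150/200 = 75.0% and 100/150 = 66.7%. Restart is then at 67% to 80% of the previous dose. Intermediate levels, which the safety monitoring committee may choose, would change these figures.

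**The case against.** The strongest reply is that the row should not be read alone. Section 8.3.3.1 ties dose adjustment to the organ system with the worst drug-related toxicity and allows time off drug for recovery. Hemoglobin is in the hematology panel (Table 10-5). Section 10.6.2 keeps scheduled tests going during an interruption and asks for them on the restart day. Section 11.3 requires discontinuation when the investigator, sponsor or medical monitor judges the risk unacceptable. A reader might infer that the protocol compels restart in a patient with unresolved Grade 4 anemia, or that nobody would notice it. The documents do not support either inference. What they support is narrower: the written test permits restart, and each safeguard rests on judgment and states no restart value.

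A second reply is that the choice was deliberate. The list that begins "Dose-limiting toxicities are drug-related AEs defined as follows" (Section 6.1.1.2) names neutropenia and thrombocytopenia but not anemia, and the row uses the same two cell lines. That is possible, but the protocol does not say so. If it was the intent, Grade 4 anemia has no hold or restart rule in Table 8-1, and clarification is still needed.

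Third, restart is not meant to mirror entry: ANC is 1.5 at entry and 1 at restart, and platelets are 100 and 75. That is right, so I put no weight on the 90 g/L entry value as a restart value.

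Fourth, Grade ≤ 2 may look strict, since Grade 3 hematologic toxicity continues at full dose. But Table 8-1 already requires fixed recovery counts after Grade 4 neutropenia or thrombocytopenia while letting Grade 3 continue, so a recovery condition for anemia follows the same pattern.

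**Conclusion.** The point holds for anemia. Followed as written, the Grade 4 row can release a hold for isolated Grade 4 anemia at the first weekly check with no hemoglobin condition. It rests on the plain scope of Table 8-1 and on the absence of any such condition elsewhere in the documents.

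The size is low. Related anemia was Grade 1-2 in all 6 affected patients of 18, a dose reduction is mandatory at restart, Part 1 is capped at 36 patients, and the SAP states that Part 2 will not be conducted. No analysis is affected.

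A reader might extend the point to every other cell line. I would not. Leukopenia and monocytopenia have no restart value of their own, but neutrophils are part of the white cell count, so ANC ≥ 1 × 10⁹/L already forces a white count of at least that. Lymphopenia with clinical consequences is also unmeasured by the row, but the documents give no evidence on which to base added restart conditions there. Nor do the data show that Grade 4 anemia is likely with this combination.

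**What to change.** Keep the ANC and platelet conditions in the Grade 4 row of Table 8-1 and add: *and, if the hold was for anemia, anemia has recovered to Grade ≤ 2*. This is the recovery grade used for nonhematologic G1T38 toxicity (Section 8.3.3.1) and for osimertinib toxicity (Section 8.3.3.2). The documents do not set a grade for anemia, so the clinical team should confirm it.

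I would not add a catch-all for other cell lines. I would also not borrow the 14-day transfusion exclusion from screening: 14/21 is two thirds of the standard off-drug allowance.

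The cost is a short amendment, which Section 14.6 requires to go to the ethics committee or review board, and possibly longer holds in rare cases. Holds beyond 21 days already need discussion with the medical monitor. If no patient remains on G1T38, carry the clause into any later protocol that reuses this table.
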